5. STATISTICAL ANALYSIS METHODS

5.1. General Considerations

Descriptive statistical methods will be used to summarize the data from this trial, with statistical testing performed for the efficacy endpoints. Unless stated otherwise, the term “descriptive statistics” refers to number of subjects (N), number of observations (n), arithmetic mean, median, standard deviation (SD), geometric mean and coefficient of variation (CV%) (for concentration data only), first quartile (Q1), third quartile (Q3), minimum, and maximum for continuous data, and frequencies and percentages for categorical data. Certain figure presentations will include the standard error of the mean (SE). The term “treatment group” refers to treatment assignment: placebo, tavapadon 5 mg, and tavapadon 15 mg. All data collected from subjects who sign the informed consent form, including screen failures, will be included in data listings. Unless otherwise noted, the data listings will be sorted first by treatment group and subject number and then by date within each subject number.

The number and proportion of missing visits and key assessments due to COVID-19 control measures and the frequency of remote assessments performed due to COVID-19 restrictions will be tabulated by treatment, visit, and assessment as well as the overall number and proportion of subjects with any such missing visits, assessments, or remote visits in each treatment group.

The statistical analyses will be conducted with the SAS® software package version 9.4 or higher.

5.2. Populations for Analyses

The analysis populations are defined [Table 4](#).

Table 4: Populations for Analysis

Population	Description	Analysis
ITT	All randomized subjects	Demographic and Baseline Characteristics
FAS	All randomized subjects who receive at least 1 dose of IMP. This will be the safety analysis set.	Safety analysis
mITT	All randomized subjects who receive at least 1 dose of IMP and have a baseline and at least one postbaseline MDS-UPDRS assessment.	Primary analysis set for efficacy
Endpoint completers	All subjects in the mITT population who have an MDS-UPDRS assessment at baseline and endpoint	Sensitivity analysis set for efficacy
PK	All randomized subjects who receive at least 1 dose of tavapadon and have at least one measurable scheduled tavapadon (CVL751) concentration	PK analysis set

Abbreviations: FAS = full analysis set, IMP = investigational medicinal product, ITT = intent-to-treat, mITT = modified intent-to-treat, PK = pharmacokinetic, MDS-UPDRS = Movement Disorder Society – Unified Parkinson’s Disease Rating Scale.

[figure not shown]

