Prolactin level		X ^u									X ^u		
Serology (HIV, HbsAg, and HCV)	X												

Table 2 Schedule of Assessments

Trial Period:	Screen	Baseline	Treatment									Safety Follow-up ^a
Trial Week:	-4 to -1	1	2	5	8	11	14	18	22	26	27 ^b	31
Trial Day:	-31 to -1	1	14±3	35±3	56±3	77±3	98±3	126±3	154±3	182±3	189±3	217±3
Visit/Contact:	Visit 1	Visit 2	Visit 3	Visit 4	Visit 5	Visit 6	Visit 7	Visit 8	Visit 9	Visit 10	Visit 11 (EOT/ET)	Telephone ^c
Dipstick urinalysis ^o	X	X				X			X		X	
Serum pregnancy test ^p	X											
Urine dipstick pregnancy test ^p		←-----→										
Urine drug screen ^q	X	←-----→									X	
Plasma PK sample ^r		X		X		X	X		X		X	
Future biospecimen research blood sample ^s		X										
IMP Administration and Compliance^t												
Dispense IMP		X	X	X	X	X	X	X	X	X		
Assess IMP compliance			X	X	X	X	X	X	X	X	X	

Abbreviations: ADL = activities of daily living, CGI-I = Clinical Global Impression – Improvement, CGI-S = Clinical Global Impression – Severity of Illness, C-SSRS = Columbia-Suicide Severity Rating Scale, ECG = electrocardiogram, eCRF = electronic case report form, EQ-5D-5L = EuroQol 5 Dimension 5 Level, ESS = Epworth Sleepiness Scale, EOT = end of treatment, ET = early termination, HbsAg = hepatitis B surface antigen, HCV = hepatitis C virus, HIV = human immunodeficiency virus, IMP = investigational medicinal product, [REDACTED], MDS-UPDRS = Movement Disorder Society – Unified Parkinson’s Disease Rating Scale, MoCA = Montreal Cognitive Assessment, PDQ-39 = 39-Item Parkinson’s Disease Questionnaire, PGIC = Patient Global Impression of Change, PK = pharmacokinetic, QUIP-RS = Questionnaire for Impulsive-Compulsive Disorders in Parkinson’s Disease-Rating Scale.

- Subjects who prematurely discontinue from the trial or who are not eligible for or choose not to participate in the open-label extension trial (Protocol CVL-751-PD-004) are to participate in the 4-week Safety Follow-Up Period. Subjects who proceed into the open-label extension trial will go directly into that trial and will not complete the Safety Follow-Up Period.
- The assessments scheduled for the Week 27 visit are to be performed for any subject who prematurely discontinues from the trial.
- Contact with subjects via telephone call or other means of communication to check on their status.
- Informed consent must be obtained before any trial-related procedures are performed.

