8.2 Efficacy Assessments

The planned time points for efficacy assessments are shown in the Schedule of Assessments ([Table 2](#)). At each clinic visit, efficacy assessments should be completed first, followed by the safety assessments.

8.2.1 *Movement Disorder Society-Unified Parkinson's Disease Rating Scale*

The MDS-UPDRS ([Goetz et al, 2008](#)) is a multidimensional scale that assesses the motor and nonmotor impacts of PD across 4 parts. The scale is completed using a combination of physician and patient assessments and a collection of information from the patient or caregiver:

- Part I, nonmotor aspects of experiences of daily living, comprises 13 items, 6 of which are rated by the physician (Part IA) and 7 of which are rated by the patient (Part IB).
- Part II, motor aspects of experiences of daily living, comprises 13 items that are rated by the patient. The 13 items in Part II and the 7 items in Part IB constitute the patient questionnaire portion of the MDS-UPDRS.
- Part III, motor examination, comprises 18 items that are assessed by the investigator (resulting in 33 scores by location and lateralization).

- Part IV, motor complications, comprises 6 item (3 items for dyskinesia and 3 items for fluctuation) and requires the physician to use historical and objective information to assess dyskinesia and motor fluctuations.

Each item is rated on a scale from 0 to 4 on which 0 = normal, 1 = slight, 2 = mild, 3 = moderate, and 4 = severe.

The same individual should perform the ratings for an individual subject throughout the course of the trial. The postbaseline MDS-UPDRS assessments will be conducted in the clinic, ~2 to ~6 hours after the subjects have taken their daily dose of IMP (at home), at the end of Weeks 5, 8, 11, 14, 18, 22, 26, and 27.

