9.3 Populations for Analyses

The analysis populations are defined in [Table 8](#).

Table 8 Populations for Analysis

Population	Description	Analysis
ITT	All randomized subjects	Demographic and Baseline Characteristics
FAS	All randomized subjects who receive at least 1 dose of IMP. This will be the safety analysis set.	Safety analysis
mITT	All randomized subjects who receive at least 1 dose of IMP and have both a baseline and at least 1 postbaseline MDS-UPDRS assessment	Primary analysis set for efficacy
Endpoint Completers	All subjects in the mITT population who have an MDS-UPDRS assessment at baseline and endpoint	Sensitivity analysis for efficacy
PK Analysis Set	All randomized subjects who receive at least 1 dose of IMP and have at least 1 measurable tavapadon (CVL-751) concentration	PK analysis

Abbreviations: FAS = full analysis set, IMP = investigational medicinal product, ITT = intent-to-treat, MDS-UPDRS = Movement Disorder Society – Unified Parkinson’s Disease Rating Scale, mITT = modified intent-to-treat, PK = pharmacokinetic.

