5.9. Primary Efficacy Analysis

5.9.1. Primary Estimand

The key research question for the primary endpoint will be addressed with an estimand based on the following attributes:

- 1) Treatments: treatments as randomized regardless of the actual treatment received or the final dose level achieved following the titration steps.
- 2) Target study population of interest: subjects in the modified intent-to-treat (mITT) population regardless the completion status of dose titration steps.
- 3) Endpoint (variable) of interest: change from baseline to Week 26 in the MDS-UPDRS Part II + III Combined Score.
- 4) Population level summary of interest: estimated mean difference between each tavapadon dose group and placebo group in the endpoint of interest.
- 5) Strategy for Intercurrent events (ICEs): a hypothetical strategy will be used to address intercurrent events (ICEs) of potential death, treatment discontinuations, missed visits/assessments, and start of prohibited concomitant Parkinson's disease medications. The data after treatment discontinuations or after the start of prohibited Parkinson's disease concomitant medications will be censored under the hypothetical strategy. Prohibited Parkinson's disease concomitant medications are defined as medications in ATC classifications of ADAMANTANE DERIVATIVES, DOPAMINE AGONISTS, MONOAMINE OXIDASE B INHIBITORS, OTHER ANTIPARKINSON DRUGS, OTHER DOPAMINERGIC AGENTS, or DOPA AND DOPA DERIVATIVES that are started after the first dose of IMP and prior to the last dose of IMP with duration of use 7 days or more. The hypothetical strategy allows the study to assess the effect of tavapadon treatment without the confounding effect of prohibited concomitant Parkinson's disease treatments.

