5.9.3.4. Impact of Missing Values Handling

Whilst every effort will be made to prevent avoidable missing values during the study conduct ([National Research Council, 2010](#)), it is unrealistic to expect no missing values in clinical trials. The impact of missing values on the analysis results will be assessed by the sensitivity analyses described below.

Under Missing at Random (MAR) Assumption

Multiple imputation (MI) will be performed to replace each missing value with a set of plausible values that represent the uncertainty about the correct value to impute. The Markov chain (MCMC) method will be utilized for the mITT set. SAS PROC MI will be used to generate 27 possible imputed datasets: Each of these datasets will be analyzed using PROC MIXED in SAS using the MMRM model as described in [Section 5.9.2](#). The results of the analyses of the datasets will be combined using PROC MIANALYZE to produce an inferential result.

Considerations of Data Potentially Missing Not at Random (MNAR)

A pattern mixture model (PMM) approach will be used to address potentially MNAR patterns. The following three patterns of subjects in the mITT set will be considered:

- 1) Subjects with no missing values from discontinuation or from initiation of prohibited Parkinson's disease concomitant mediation during treatment period.
- 2) Subjects with missing values from the types of ICEs below will be considered having MNAR
 - a. Subjects who discontinue due to reasons, as recorded on the eCRF, of lack of efficacy, adverse events associated with motor symptoms of Parkinson's disease, physician decision, and withdrawal by subject.
 - b. Subjects who initiated concomitant Parkinson's disease medications (ATC classifications of ADAMANTANE DERIVATIVES, DOPAMINE AGONISTS, MONOAMINE OXIDASE B INHIBITORS, OTHER ANTI-PARKINSON DRUGS, OTHER DOPAMINERGIC AGENTS, or DOPA AND DOPA DERIVATIVES) after the first dose of IMP and prior to the last dose of IMP with a use duration of 7 days or more will be considered having a potential confounding ICE. The efficacy data post ICE will be treated as missing with the missing pattern of MNAR.

The MNAR cases will be identified and documented prior to database lock and unblinding ([Section 9.5](#)).

- 3) Subjects with missing values from the type of ICEs below will be considered as having MAR

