5.10.2.2. Sensitivity Analyses

The sensitivity analyses described in [Section 5.9.3](#) for the primary estimand will also be performed for the secondary efficacy estimand 2 except for the sensitivity analyses to assess the impact of missing value handling. For the secondary efficacy estimand 2, the case of potential MNAR will be imputed as “non-responder” for the sensitivity analysis. No additional sensitivity analysis under the MAR assumption using multiple imputations will be performed. In addition, a sensitivity analysis excluding the PGIC score obtained remotely may be performed if such remote assessments are conducted due to COVID-19 restrictions.

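### The MNAR sensitivity analyses leave out dosed subjects who have no post-baseline MDS-UPDRS

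*SAP*

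**What the plan says.** **Analysis set.** SAP 5.2 defines mITT as "All randomized subjects who receive at least 1 dose of IMP and have a baseline and at least one postbaseline MDS-UPDRS assessment". Protocol 9.3 has the same rule: subjects must "have both a baseline and at least 1 postbaseline MDS-UPDRS assessment". The primary estimand (SAP 5.9.1) takes as its population "subjects in the modified intent-to-treat (mITT) population regardless the completion status of dose titration steps", and both key secondary estimands (5.10.1, 5.10.2) do the same.

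**Timing.** Protocol 8.2.1 places the post-baseline MDS-UPDRS "at the end of Weeks 5, 8, 11, 14, 18, 22, 26, and 27". The Week 2 visit has none.

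**Early leavers.** A footnote to the schedule in Protocol 1.3 says: "The assessments scheduled for the Week 27 visit are to be performed for any subject who prematurely discontinues from the trial". Those assessments include MDS-UPDRS and PGIC. Under the hypothetical strategy in SAP 5.9.1, "The data after treatment discontinuations or after the start of prohibited" Parkinson's medication will be censored.

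**MNAR analyses.** SAP 5.9.3.4 opens its pattern-mixture approach with "The following three patterns of subjects in the mITT set will be considered". The MNAR class covers stopping for lack of efficacy, for a motor-symptom adverse event, by physician decision or by the subject's own withdrawal, and starting a Parkinson's drug for 7 days or more. MNAR cases on active drug are imputed by J2R; those on placebo are imputed as MAR. Adverse events unrelated to motor symptoms, loss to follow-up and non-compliance are MAR in all arms. For PGIC, SAP 5.10.2.2 says "the case of potential MNAR will be imputed as" non-responder.

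**No wider set.** The summaries in SAP 5.11 and 5.12 list no efficacy analysis on FAS or ITT.

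**The concern.** Membership of mITT depends on something that happens after randomisation. For the main MMRM this costs little, because a subject with only a baseline value contributes no post-baseline data to that model.

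The imputation analyses differ, because a baseline-only subject can be imputed. The MAR code in SAP 9.6.1 includes treatment and the baseline score, and the J2R call in 9.6.2 carries baseline as a covariate. An active-arm subject who withdrew before Week 5 would take placebo-like values under J2R, or count as a PGIC non-responder. Leaving that subject out removes the penalty.

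For J2R the direction does not depend on unequal dropout between arms. Only active-arm MNAR cases are moved to placebo behaviour, so omitting them can only raise the expected difference when the drug works. At stake is how far analyses offered as evidence of robustness can be relied on.

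**Working it through.** **1. The plan's own figure.** Inputs from SAP 1.2: difference 4, SD 9, two-sided alpha 0.025, power 90%, dropout 27%. With n = 2(z₁₋α/₂ + z₀.₉₀)² × SD² / difference², n = 126 by the normal approximation and 127 using the t distribution. 127 / 0.73 = 174 per arm, as stated. The planned dropout is 0.27 × 174 ≈ 47 per arm. (Protocol 9.2 gives alpha 0.05; that difference does not bear on this point.)

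**2. Early leavers.** The documents give no dropout timing. Assuming a constant rate over 27 weeks:

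- share gone by Week 5 = 1 − 0.73^(5/27) = 5.7%
- 0.057 × 174 ≈ 10 per arm

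This assumes that none has a termination MDS-UPDRS, so at a constant rate it is an upper figure. Dropout concentrated early would raise it.

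**3. J2R.** Assume a difference of 4 in subjects not imputed by J2R and 0 in active-arm subjects who are. Let d = 0.27, e = share excluded from mITT, and m = share of dropouts classed MNAR.

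- On mITT: 4 × [1 − m(d − e)/(1 − e)]
- On FAS: 4 × (1 − m·d)

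With e = 0.057:

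- m = 1: mITT 4 × (1 − 0.213/0.943) = 3.10; FAS 4 × 0.73 = 2.92; gap 0.18
- m = 0.5: mITT 3.55; FAS 3.46; gap 0.09

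Because the excluded share is unknown, the range is:

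| Share of dropouts with no post-baseline MDS-UPDRS | Excluded per arm | mITT, m = 1 | Gap to FAS (2.92) | mITT, m = 0.5 | Gap to FAS (3.46) |
|---|---|---|---|---|---|
| 0% | 0 | 2.92 | 0 | 3.46 | 0 |
| 10% | 5 | 3.00 | 0.08 | 3.50 | 0.04 |
| 25% | 12 | 3.13 | 0.21 | 3.57 | 0.11 |
| 50% | 23 | 3.38 | 0.46 | 3.69 | 0.23 |

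**4. PGIC non-responder analysis.** Response rates are not in the documents. Assume 50% on active and 30% on placebo within mITT, a difference of 20 points. If 5.7% per arm are excluded and all are MNAR-class, adding them as non-responders gives 0.943 × 50 − 0.943 × 30 = 18.9 points. With fewer MNAR cases the difference stays between 18.9 and 20.

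With unequal exclusions fA (active) and fP (placebo), the change is −50·fA + 30·fP. At these rates the difference shrinks if fA exceeds 0.6·fP and grows otherwise. The direction is therefore not fixed for PGIC as it is for J2R.

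**The case against.** **Termination visits keep many early leavers in.** The mITT rule does not require the qualifying MDS-UPDRS to be on treatment, and early leavers are due one. This stands, and it limits the problem to subjects with no post-baseline MDS-UPDRS at all. It is not a full answer. Protocol 7.3 asks for continued assessments only if possible. A termination visit on Days 2 to 24 maps to Week 2 (SAP 4.2), where no MDS-UPDRS is scheduled, and the SAP does not say how a subject with only that value is handled.

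**A reader might infer that the MNAR analyses cannot test the dropout they were designed for.** The documents do not support that. Every MNAR-class dropout after a first MDS-UPDRS is still imputed by J2R or as a non-responder. In the table, even with half of all dropouts excluded, about 23 per arm remain in mITT.

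**A reader might infer that the omission hides intolerance during titration on active drug.** The documents do not support that either. Protocol 2.3 links titration speed to nausea, orthostatic blood pressure changes and fatigue. Such events would ordinarily count as unrelated to motor symptoms, so SAP 5.9.3.4 would keep them MAR even in a larger set. No dropout timing by arm is given, and the 5 mg dose is reached only on Day 41 (Protocol 4.1.2), after the Week 5 visit. The subjects affected are those with MNAR-class reasons, such as early withdrawal by the subject or physician decision.

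**A reader might put the J2R effect at 3.8 instead of 4.0**, from 4 × (1 − 0.057). That treats the mITT result as undiluted and ignores J2R on later dropouts.

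**These are sensitivity analyses outside the alpha hierarchy, and the estimands name mITT.** Both statements are true, and they are why the main analyses should stay as they are. SAP 5.6 also reports disposition by arm and the size of each analysis set, so the exclusions will be partly visible. It does not commit to tabulating mITT exclusions by arm and reason.

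**Conclusion.** The point holds in a limited form. Dosed subjects with no post-baseline MDS-UPDRS fall outside every planned efficacy analysis, including the two MNAR analyses. For J2R the omission favours an effective drug. Under constant-rate dropout and no termination visits, the size is about 0.1 to 0.2 points of a 4-point effect, and less if termination visits are well attended. It reaches 0.46 only if half of all dropouts lack a post-baseline MDS-UPDRS and every dropout is MNAR. For PGIC, equal exclusions of 5.7% would reduce an assumed 20-point difference to no less than 18.9; unequal exclusions could move it either way.

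Dropout timing, the MNAR share and the PGIC response rates are all assumptions. The primary analysis, the alpha allocation and trial conduct are unaffected. This is a cheap improvement with a modest effect.

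**What to change.** - Keep mITT for the main MMRM and GLIMMIX analyses.
- Run the pattern-mixture analysis in SAP 5.9.3.4 and the PGIC non-responder analysis in 5.10.2.2 on all randomised, dosed subjects with a baseline value (for PGIC, which has no baseline score, a baseline MDS-UPDRS).
- Apply the SAP's existing discontinuation-reason rules to baseline-only subjects, and state that for J2R the last observed time point is then baseline. Subjects who stopped for adverse events unrelated to motor symptoms stay MAR.
- State how a subject is handled whose only post-baseline MDS-UPDRS is a termination visit mapped to Week 2.
- Tabulate subjects excluded from mITT by arm and discontinuation reason.

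The cost is SAP wording, minor programming (checking that the imputation code accepts subjects with every post-baseline value missing) and slightly less favourable sensitivity estimates.

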5.3. Statistical Hypotheses

The primary and key secondary hypotheses are summarized below. All will be tested based on 2-sided α .

Primary Endpoint	Tavapadon 15 mg QD vs Placebo	Tavapadon 5 mg QD vs Placebo
Change from baseline to endpoint in MDS-UPDRS Part II and III combined score	$H_1 : \mu_{\text{active}} = \mu_{\text{placebo}}$ vs $\mu_{\text{active}} \neq \mu_{\text{placebo}}$	$H_2 : \mu_{\text{active}} = \mu_{\text{placebo}}$ vs $\mu_{\text{active}} \neq \mu_{\text{placebo}}$
Key Secondary Endpoints		
Change from baseline to endpoint in the MDS-UPDRS Part II score	$H_3 : \mu_{\text{active}} = \mu_{\text{placebo}}$ vs $\mu_{\text{active}} \neq \mu_{\text{placebo}}$	$H_5 : \mu_{\text{active}} = \mu_{\text{placebo}}$ vs $\mu_{\text{active}} \neq \mu_{\text{placebo}}$
Proportion of responders on the PGIC at endpoint	$H_4 : \pi_{\text{active}} = \pi_{\text{placebo}}$ vs $\pi_{\text{active}} \neq \pi_{\text{placebo}}$	$H_6 : \pi_{\text{active}} = \pi_{\text{placebo}}$ vs $\pi_{\text{active}} \neq \pi_{\text{placebo}}$

5.4. Multiplicity Adjustment

A graphical approach depicted below is utilized to illustrate the hierachal multiple testing strategy planned for the hypotheses described above to control the overall Type I error rate. The primary endpoint of the tavapadon 15 mg QD will be compared with that of placebo (H_1) with full α of 0.05 and, if successful, the available α will be passed along fully ($r=1$) to the comparison of the primary endpoint of tavapadon 5 mg QD with placebo (H_2). If H_2 is successful, the full α will be available to the secondary hypothesis H_3 . The sequence will continue until H_6 or until the sequence breaks with no α remaining available.

5.5. Strata and Covariates

The randomization is stratified by concurrent use of MAO-B inhibitor. This factor is planned to be included as a covariate in the efficacy analyses. However, due to isolated administrative errors at a few sites during randomization through IRT system, 15 subjects were randomized to the incorrect strata (3 non-MAO-B inhibitor users were randomized to the MAO-B inhibitor use stratum and 12 MAO-B inhibitor users were randomized to the non-user stratum; details in [Section 9.7](#)). The actual MAO-B inhibitor use status, as recorded in eCRF, will be used as a covariate instead of the randomization strata in these cases.

The baseline value of each efficacy variable (if applicable) will also be included as a covariate in the efficacy analyses.

5.6. Subject Disposition, Demographic and Baseline Characteristics

Subject disposition will be based on the ITT population with tabulation of the number of subjects who complete the study and the number of discontinued and from the study and the reasons by treatment group. Additionally, the number of days on study will be summarized.

Tabulation of subject randomization by country and site will be presented for the ITT population and for completed subjects. A listing of randomization number, subject, treatment randomized, country, and site will be provided. Further tabulation by region (United States, Non-US) and country will also be presented. Subject disposition data will also be tabulated for all subjects screened to include the number of subjects screened, the number of screen failures, and the reason for screen failure.

Kaplan-Meier plots will be used to assess time to discontinuation of study treatment, time to discontinuation of treatment due to adverse events, and time to discontinuation of treatment due to subject withdrawal. The complete subjects or subjects discontinued treatment for reasons other than adverse events and withdrawal of consent will be censored at the time of end of treatment for the respective KM analyses. If a subject died without treatment discontinuation date information, date of death will be used as the time of discontinuation.

Number of subjects in each analysis population set will be summarized.

Demographic data and baseline characteristics including age, age categorical distribution, sex, childbearing potential, race, ethnicity, height at screening, weight at screening and at baseline, BMI at screening and at baseline, MAO-B inhibitor use at baseline, history of Parkinson's disease (including years from initial diagnosis), Montreal Cognitive Assessment (MoCA) total score, Modified Hoehn & Yahr assessment at screening, MDS-UPDRS (all parts, Part I + Part II + Part III combined, and Part II + III combined) score at baseline, and CGI-S at baseline will be summarized using descriptive statistics for the ITT population. Further tabulation by region and country will also be presented.

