1.2. Sample Size Considerations

A sample size of 174 subjects per group will provide 90% power to detect a change in the primary outcome measure (change from baseline to endpoint in the MDS-UPDRS Parts II and III combined score) of 4 points, with a standard deviation of 9, 2-sided alpha level = 0.025, and assuming a 27% dropout rate.

In the event of higher than anticipated early terminations due to COVID-19 or other reasons, Cerevel may extend enrollment in order to maintain the planned statistical power.

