5.8. Exposure to Treatment

The number of days on study drug, reasons for premature discontinuation of IMP, treatment compliance, days in each phase (Titration and Maintenance), and average dose in each phase, will be summarized by treatment group for the FAS Population. Exposure data, including dose level as received, will be listed.

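### The Kaplan-Meier plots for stopping due to adverse events and due to withdrawal censor competing reasons, so one minus the curve overstates the probability of stopping for that reason, by about one point at the planned dropout

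*SAP*

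**What the plan says.** SAP section 5.6 states that "Kaplan-Meier plots will be used to assess time to discontinuation of study treatment". It adds two cause-specific plots, "time to discontinuation of treatment due to adverse events, and time to discontinuation of treatment due to subject withdrawal". One sentence gives the censoring rule for all of them: completers, and subjects whose reason for stopping was neither an adverse event nor withdrawn consent, "will be censored at the time of end of treatment for the respective KM analyses". A death without a recorded stop date counts as a discontinuation at the date of death. The SAP names no cumulative incidence function or other competing-risk estimate.

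Reasons for stopping are also reported as simple counts. Section 5.6 tabulates, for the ITT population, the number of subjects "discontinued and from the study and the reasons by treatment group". Section 5.8 summarizes by treatment group, for the FAS, the "reasons for premature discontinuation of IMP, treatment compliance" and exposure. Section 5.14.1 adds summaries of the adverse events that led to stopping treatment, including by preferred term and phase at onset.

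No test is attached to the curves. Section 5.1 describes the analysis as descriptive, "with statistical testing performed for the efficacy endpoints".

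**The concern.** Kaplan-Meier treats a censored subject as someone who could still have the event later. That suits a subject whose observation simply ends. It does not suit one who has already stopped treatment for another reason and so can never stop it for an adverse event. With such subjects censored, one minus Kaplan-Meier estimates how many would stop for adverse events if no other reason for stopping existed. The proportion who actually stop for adverse events is the cumulative incidence, and one minus Kaplan-Meier is never below it.

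Competing exits are to be expected. Protocol section 7.3 lists nine reasons for stopping, and SAP section 5.9.3.4 names others, such as loss to follow-up and site termination.

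What is at stake is how tolerability by dose is presented. Safety and tolerability of the two fixed doses is a stated objective, and an adverse event that leads to discontinuation is an event of special interest. These plots are the planned display of when such stops occur. A reader who takes a probability from the curve will get a figure that differs from the tables in the same report.

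**Working it through.** **The plan's own figure.** The SAP gives no number for these curves. Its only use of a dropout rate is the sample size in section 1.2 ("assuming a 27% dropout rate"). With a 4-point difference, SD 9, two-sided alpha 0.025 and 90% power, the t-based calculation gives 127 evaluable subjects per group, and 127 / 0.73 = 173.97, so 174. The figure reproduces, and 27% can be taken as total dropout. (Protocol section 9.2 gives alpha 0.05 for the same 174; that is a separate matter.)

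**Inputs.**
- Total dropout T: 27%, from SAP section 1.2. Other values of T are assumptions.
- Share s of dropout due to the plotted reason: not in the documents; assumed 20% to 80%.
- Cause-specific hazards: assumed proportional over the 27 weeks.
- Censoring time: taken as the subject's own end of treatment.

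**Formulas.** Cumulative incidence = T × s. One minus Kaplan-Meier, other reasons censored = 1 − (1 − T)^s.

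| T | s | Cumulative incidence | 1 − KM | Excess (points) |
|---|---|---|---|---|
| 27% | 20% | 5.40% | 6.10% | 0.70 |
| 27% | 50% | 13.50% | 14.56% | 1.06 |
| 27% | 80% | 21.60% | 22.26% | 0.66 |
| 40% | 20% | 8.00% | 9.71% | 1.71 |
| 40% | 50% | 20.00% | 22.54% | 2.54 |
| 40% | 80% | 32.00% | 33.55% | 1.55 |

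At T = 15% the excess is 0.2 to 0.3 points. A simulation with 174 subjects per arm, 27% dropout and an even split gave 13.6% against 14.6%, in line with the table.

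**Timing.** At 27% with an even split, if every competing exit came before every event of interest, the curve would end at 13.5 / (100 − 13.5) = 15.6%, an excess of 2.1 points. If every competing exit came last, the excess would be zero.

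**Comparison between arms.** With the same even split in each arm, more dropout gives more excess: 0.56 points at 20%, 1.06 at 27%, 2.54 at 40%. With different splits the order can reverse (assumed figures):
- 28% dropout, of which 25% adverse events and 3% other: 1 − 0.72^(25/28) = 25.4%, excess 0.4 points.
- 22% dropout, of which 8% adverse events and 14% other: 1 − 0.78^(8/22) = 8.6%, excess 0.6 points.

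The absolute excess is roughly half the product of the cumulative hazards of the plotted and the competing reasons, so it depends on both.

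**Sum of the two curves.** Assume 27% dropout made up of 10% adverse events, 10% withdrawal and 7% other. Each cause-specific curve ends at 1 − 0.73^(10/27) = 11.0%. Together they reach 22.0%, below the all-cause 27%.

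**The case against.** The strongest reply is that little depends on these plots. They are descriptive, and no hypothesis, alpha, estimand or decision rule uses them. The crude proportions by reason are already planned in SAP sections 5.6, 5.8 and 5.14.1. The SAP nowhere says that one minus Kaplan-Meier will be reported as the probability of stopping for a given reason, and a curve with other causes censored is a legitimate description of the cause-specific hazard. The excess at 27% is about one point, against a standard error of about 2.6 points for a proportion of 13.5% in 174 subjects (√(0.135 × 0.865 / 174) = 0.026). All of this stands, and it limits the importance of the point. It does not make Kaplan-Meier the right estimator of absolute risk over time, which is how most readers take such a plot, and the tables of totals by reason do not supply a corrected time course.

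The wording also leaves room. The censoring sentence does not expressly say that withdrawals are censored in the adverse-event plot, or the reverse; the word respective implies it. If the end of treatment meant the planned Day 189 and not the subject's own last day, subjects with competing exits would stay in the risk set and the excess would vanish. The subject's own date is the natural reading, but the text should settle it.

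A reader might infer that the overstatement must be larger in the arm with more dropout, or that the two cause-specific curves must add to more than the all-cause curve. Neither follows. The documents give no split by reason or arm, the arm ordering can reverse, and the sum is bound to be too large only when every cause is plotted, whereas the SAP plots two.

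**Conclusion.** The point holds for the two cause-specific plots and is minor. On the natural reading of section 5.6, one minus Kaplan-Meier is never below the cumulative incidence and exceeds it whenever a competing exit precedes an event of interest. At the planned 27% dropout the excess is about 0.7 to 1.1 points, and up to 2.1 with an even split and the least favourable timing. If total dropout were 40% it would be about 1.55 to 2.54 points. These sizes rest on assumed splits and, apart from the timing bound, on proportional hazards.

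The excess can differ between arms, according to the amount and timing of competing-reason dropout and the rate of the plotted reason. The documents do not allow its direction to be predicted. The all-cause curve is not affected, since it has no competing reason, and neither is any efficacy test. Nothing here supports a claim that the trial's tolerability conclusions are biased: the tabulated proportions are unaffected.

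**What to change.** In SAP section 5.6:
- Keep Kaplan-Meier for all-cause discontinuation.
- For the adverse-event plot and the withdrawal plot, use Aalen-Johansen cumulative incidence functions by treatment group. Count every other reason for stopping as a competing event, including withdrawal in the adverse-event plot and adverse events in the withdrawal plot.
- Censor only completers, at their own end of treatment, and say so in place of the single sentence that now covers all three plots.

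The curve endpoints should then agree with the reasons for stopping treatment in section 5.8, apart from any difference in analysis population and the few days' spread in completers' last doses. The reasons are already recorded on the eCRF, so no new data are needed. The cost is a few lines of SAP text and a change of estimator in the plotting program, with no effect on sample size, alpha or the efficacy analyses.
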